## **5 Statistical Analysis Datasets**

### **5.1 Analysis Sets**

- Enrolled set (ES):  
Subjects from whom informed consent has been obtained (including screen failures)
- Randomized set (RS):  
Randomized subjects in the ES
- Safety set (SS):  
Subjects in the RS who receive the IMP at least once
- Full Analysis set (FAS):  
Subjects in the SS who have at least 10 days of baseline and post baseline efficacy assessment data on monthly average number of headache days of at least moderate severity
- Pharmacokinetic Analysis set:  
The pharmacokinetic analysis set will include all subjects in whom at least 1 dose of TEV-48125 is administered, and date and time of blood sampling for plasma drug concentration is recorded for at least 1 time point after TEV-48125 dosing.

- Immunogenicity Analysis set:  
The immunogenicity analysis set will include all subjects in whom at least 1 dose of TEV-48125 is administered, and date and time of blood sampling for serum ADA assessment is recorded for at least 1 time point after TEV-48125 dosing.

For all analysis sets except for ES, treatment will be assigned based on the treatment to which subjects are randomized regardless of which treatment they actually received.

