## **7.1 Subject Disposition**

Data will be summarized for the overall population and by country.

The number of subjects from whom informed consent has been obtained, screen failure subjects and randomized subjects will be provided for the ES.

The number and percentage of subjects in whom IMP is administrated, in whom IMP is not administrated, who completed the trial and who are withdrawn from the trial will be summarized by treatment group, for all TEV-48125-treated subjects, and overall for the RS. The primary reason for discontinuation will also be summarized by treatment group, for all TEV-48125-treated subjects, and overall for the RS.

The number and percentage of subjects who are included in the SS, FAS, pharmacokinetic analysis set, immunogenicity analysis set, and who are excluded from the SS, FAS, pharmacokinetic analysis set, immunogenicity analysis set will be summarized by treatment group, for all TEV-48125-treated subjects, and overall for the RS.

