## **7.6 Protocol Deviations**

The number and percentage of subjects with any major protocol deviations and each classification will be provided in each trial site and overall site by treatment group, for all TEV-48125-treated subjects, and overall for the RS.

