The endpoint 5) will be compared between the combined TEV-48125 group and the placebo group, since the patients randomized to both active treatment arms receive the

same dose of TEV-48125 675 mg at first dose of IMP. Similar analyses described in [Section 8.1](#) will be used. An MMRM will be used to estimate the mean change from baseline by week (ie, for Week 1, Week 2, Week 3 and Week 4) after the first dose of IMP, and an ANCOVA model and Wilcoxon rank-sum test will be used to estimate the mean change from baseline for Month 1 after the first dose of IMP.

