## 9 Safety Analyses

The SS will be used for all safety analyses. Summaries will be presented by treatment group and all TEV-48125 groups unless specified otherwise. Descriptive statistics will include number of subjects, mean, SD, median, minimum, and maximum.

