### **10.4 Statistical Analysis Method**

Concerning [10.1](#)Endpoint, descriptive statistics will be calculated by treatment group for each blood sampling time point. Descriptive statistics include the number of subjects,

arithmetic mean, standard deviation, coefficient of variation, minimum, median, and maximum.

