## **14 Changes in the Planned Analyses**

- Wilcoxon rank-sum test is conducted as the sensitivity analysis for normality assumption of the residuals in the primary efficacy analysis.
- The sensitivity analysis based on multiple imputation method is conducted to explore the impact of missing data in the primary efficacy analysis.
- MMRM analysis is added to estimate the mean change from baseline in the monthly number of headache days of at least moderate severity for the overall 3 months treatment period and by each month.
- The definitions of pharmacokinetic analysis set and immunogenicity analysis set were changed as described in Section 5.1. Pharmacokinetic analysis set and immunogenicity analysis set will be determined based on the TEV-48125 dosing and the presence of recording of the date and time of blood sampling, not based on the IMP dosing and the presence of the measured values as described in the protocol.

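### SAP Section 5.1 labels the Safety and PK sets by randomized arm whatever was given, so a placebo subject given TEV-48125, or an active subject given only placebo, has adverse events summarised under a treatment not received

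*SAP*

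**What the plan says.** Section 5.1 ends with one labelling rule for all sets other than the Enrolled set: "treatment will be assigned based on the treatment to which subjects are randomized regardless of which treatment they actually received". It therefore covers the Randomized set (RS), Safety set (SS), FAS, PK set and immunogenicity set alike.

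The later sections use these labels without changing them:

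- Section 9 uses the SS for all safety analyses and says "Summaries will be presented by treatment group and all TEV-48125 groups unless specified otherwise". Nothing in Sections 9.1 to 9.8 brings in actual treatment.
- Section 5.1 defines PK membership by dosing received: "The pharmacokinetic analysis set will include all subjects in whom at least 1 dose of TEV-48125 is administered", together with a recorded sampling date and time after dosing.
- Section 10.4 says that "descriptive statistics will be calculated by treatment group for each blood sampling time point".
- Section 14 changes membership of two sets ("Pharmacokinetic analysis set and immunogenicity analysis set will be determined based on the TEV-48125 dosing") but leaves the label alone.
- The titles in Appendices 5 and 6 name no actual-treatment grouping.

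**The concern.** Labelling by randomized arm protects the efficacy comparison. Safety and concentration summaries have a different purpose: they describe what happened to people who were given a particular product. Section 5.1 foresees a mismatch between treatment assigned and treatment received, and resolves it in the same way for both purposes.

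Two kinds of error put safety data under a treatment not received. A placebo-randomized subject given TEV-48125 has adverse events counted under placebo. An active-randomized subject given only placebo has them counted under TEV-48125. For events that the drug makes more frequent, both dilute the drug-placebo difference on average. For a single rare event, the tabulated difference can move either way.

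In the PK set, membership and label follow different principles. A placebo-randomized subject can enter only by having received TEV-48125, and is then summarised as placebo.

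**Working it through.** The SAP gives no figure on this point and no expected number of dosing errors. Section 4 supplies the denominators: 180 subjects per arm, so 360 in the pooled TEV-48125 column. I assume that all are dosed.

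**Step 1: is there an override?** Reading Section 5.1 against Sections 7, 9, 10 and 14 and Appendices 5 and 6, I find none. The exception clause in Section 9 is never used to introduce actual treatment. The column for all TEV-48125-treated subjects in Section 7 is a pooled column in RS summaries and does not redefine the label for the SS or PK set.

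**Step 2: largest shift per error in a placebo-arm incidence.** Suppose k other placebo-column subjects have the event.

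- Placebo-randomized subject given drug, with the event: (k+1)/180 as randomized against k/179 as treated. The gap is (179 - k)/(180 × 179), at most 1/180 = 0.56 points.
- Same subject without the event: k/180 against k/179. The gap is k/(180 × 179), again at most 1/180.
- Active-randomized subject given only placebo, with the event: k/180 against (k+1)/181. The gap is (180 - k)/(180 × 181), at most 1/181 = 0.55 points.
- Same subject without the event: k/180 against k/181. The gap is k/(180 × 181), again at most 1/181.

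**Step 3: one error and one event in the whole table (pooled minus placebo).**

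| Subject with the event | As randomized | As treated |
|---|---|---|
| Placebo-randomized, given TEV-48125 | 0/360 - 1/180 = -0.56 points | 1/361 - 0/179 = +0.28 points |
| Active-randomized, given only placebo | 1/360 - 0/180 = +0.28 points | 0/359 - 1/181 = -0.55 points |

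The sign reverses in both rows.

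**Step 4: expected dilution for a common event.** Assume true incidences of 30% on drug and 20% on placebo, a difference of 10 points (these are not SAP figures). With d errors, the expected tabulated difference is:

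- placebo to active: 10 × (1 - d/180). For d = 0, 1, 2, 5 this is 10.00, 9.94, 9.89 and 9.72 points.
- active to placebo only: 10 × (1 - d/360). For the same d this is 10.00, 9.97, 9.94 and 9.86 points.

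**Step 5: the PK set.** By the Section 5.1 membership rule, a correctly dosed placebo subject is outside the set. Any subject labelled placebo in a Section 10.4 summary must therefore have been misdosed.

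**Step 6: can treatment received always define a regimen?** No. Section 3.2 gives both active arms 675 mg at V2, and Section 8.3.1 relies on their having the "same dose of TEV-48125 675 mg at first dose of IMP". An active subject who stops after V2 fits both regimens, so a blanket as-treated label would fail for early stops. The V2 dose is also three syringes, so an error can affect only some of them.

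**The case against.** The strongest reply is that the rule is explicit and pre-specified, bites only if a dosing error occurs, and has small effects by the figures above. Kits are numbered and assigned through the IRT, and trial personnel give the injections. Nothing in the SAP suggests that errors will be frequent. The safety tables are descriptive. All of this stands, and it limits the weight of the point.

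The second reply is traceability, and it also largely stands:

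- Serious events, discontinuation events and deaths are listed by subject (CT-9.1 to CT-9.3), as are the events of special interest (CT-9.4 to CT-9.8).
- AE-1 lists treatment-emergent events, SMED-1 lists drug administration, and PKT-X.1.4.1 gives individual concentrations.
- Section 7.1 counts set membership by arm (those "who are excluded from the SS, FAS, pharmacokinetic analysis set, immunogenicity analysis set will be summarized by treatment group"), and Section 7.6 tabulates "The number and percentage of subjects with any major protocol deviations" by treatment group.

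A reader could therefore match a rare serious event to the product given, and a non-empty placebo row in the PK summary would itself signal misdosing. None of this moves the subject to the right summary column.

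A reader might infer that any active/placebo error puts data under a treatment not received. The SAP does not support that. A 675/225/225 mg subject given placebo in error at V3 alone still received TEV-48125 and belongs in the pooled column. Swaps between the two active regimens leave the placebo and pooled columns unchanged and touch only the per-regimen summaries.

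A reader might also want every misdosed subject forced into a regimen column, for example by whether any active dose was given at V3 or V4. That repeats the fault: a placebo subject given one active syringe at V3 would sit under a regimen whose 675 mg first dose was never received.

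**Conclusion.** The point holds, with limited weight. Section 5.1 fixes a label for the SS and PK set that is wrong for a subject given the opposite product, and nothing later corrects it.

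The size depends on an unknown number of errors. With none it is zero. Each error shifts a placebo-arm incidence by at most 0.56 points, and the dilution for common events is small. It matters most for rare serious events, where one case can reverse the sign of a tabulated difference, and for the internal mismatch in the PK set. These figures assume full arms of 180 and subjects whose whole course counts as the other treatment.

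The documents do not support reading this as a threat to the efficacy results, where the as-randomized label is appropriate, or as concealment of dosing errors, which the listings would show. It should be changed because the remedy is cheap and is credible only if fixed before unblinding.

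**What to change.** In Section 5.1, limit the unconditional as-randomized rule to the RS and FAS. For the SS and PK set, state before unblinding that:

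1. The randomized label is the default, including for subjects who stop early.
2. Treatment actually received is used where the administration data (the source for SMED-1) document that a different treatment was given.
3. Any subject who received TEV-48125 counts in the pooled TEV-48125 column, and a subject who received none counts under placebo.
4. Subjects whose doses, because of an error, match no single planned regimen are listed individually, with event timing relative to first active dose, and are left out of the by-regimen PK summaries. This includes partial errors among the V2 syringes.

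Efficacy analyses stay as they are. No change is proposed for the immunogenicity set, because Section 1 places that analysis in the bioanalytical protocol, which is not at hand.

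The cost is a short rewrite of one rule, one derived actual-treatment variable and one small listing. If mixed-dosing subjects exist, the two regimen columns may not sum exactly to the pooled column. Some of those subjects' events from before their first active dose will be counted under TEV-48125, which the timing listing makes visible.

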## **5.2 Handling of Missing Data**

Information on missing data is handled within the analysis sections.

## **6 Primary and Secondary Endpoints:**

### **6.1 Primary Endpoints**

- Mean change from baseline in the monthly\* average number of headache days of at least moderate severity during the 12-week period after the first dose of IMP  
\* “the monthly” is defined as “28-day” in this trial.

### **6.2 Secondary Outcome Variables**

- Mean change from baseline in the monthly average number of migraine days during the 12-week period after the first dose of IMP
- Proportion of subjects reaching at least 50% reduction in the monthly average number of headache days of at least moderate severity during the 12-week period after the first dose of IMP
- Mean change from baseline in the monthly average number of days with use of any acute headache medications during the 12-week period after the first dose of IMP
- Mean change from baseline in the monthly average number of headache days of at least moderate severity during the 12-week period after the first dose of IMP in subjects not receiving concomitant preventive migraine medications
- Mean change from baseline in disability score, as measured by the HIT-6, at 4 weeks after the final (third) dose of IMP

## **7 Disposition and Demographic Analysis**

Descriptive statistics include number of subject (n), mean, standard deviation (SD), median, minimum, and maximum.

## **7.1 Subject Disposition**

Data will be summarized for the overall population and by country.

The number of subjects from whom informed consent has been obtained, screen failure subjects and randomized subjects will be provided for the ES.

The number and percentage of subjects in whom IMP is administrated, in whom IMP is not administrated, who completed the trial and who are withdrawn from the trial will be summarized by treatment group, for all TEV-48125-treated subjects, and overall for the RS. The primary reason for discontinuation will also be summarized by treatment group, for all TEV-48125-treated subjects, and overall for the RS.

The number and percentage of subjects who are included in the SS, FAS, pharmacokinetic analysis set, immunogenicity analysis set, and who are excluded from the SS, FAS, pharmacokinetic analysis set, immunogenicity analysis set will be summarized by treatment group, for all TEV-48125-treated subjects, and overall for the RS.

## **7.2 Demographic and Baseline Characteristics**

Data will be summarized for the overall population and by country.

The following demographic and baseline characteristics will be summarized by treatment group, for all TEV-48125-treated subjects, and overall for the RS. Continuous variables will be summarized using descriptive statistics. Categorical variables will be summarized using number and percentage of subjects.

- Age ( $[\leq 45, \geq 46 \text{ to } \leq 64, \geq 65]$ ,  $[\leq 45, > 45]$ ), sex
- Country, ethnicity, detailed ethnicity (Japanese, Korean), race
- Weight, height, body mass index
- Use of preventive migraine medication at baseline (yes, no)
- Years since onset of migraines

Medical history and complications will be coded by system organ class (SOC) and Medical Dictionary for Regulatory Activities (MedDRA Ver. 22.0) preferred term (PT). The number and percentage of subjects with medical history and complications will be summarized by SOC and PT for the RS. Subjects are counted only once in each SOC and only once in each PT.

## **7.3 Baseline Disease Evaluation**

Data will be summarized for the overall population and by country.

The following baseline disease evaluation will be summarized by treatment group, for all TEV-48125-treated subjects, and overall for the RS. Continuous variables will be summarized using descriptive statistics. Categorical variables will be summarized using number and percentage of subjects.

- Number of headache days of any duration and any severity
- Number of migraine days
- Number of headache days of at least moderate severity
- Use of any acute headache medications (yes/no)
- Use of migraine-specific acute headache medications (triptans and ergot compounds) (yes/no)

The baseline value will be calculated using all data collected from the day of V1/Screening through the day before V2/Baseline and normalized to 28 days (ie, if the number of days from V1/Screening through the day before V2/Baseline is greater or less than 28 days, the baseline value will be normalized to 28 days, see [Technical Computational Details for Primary Analysis 8.1.4](#)) using the electronic headache diary data collected through the corresponding headache diary questions.

#### **7.4 Treatment Compliance**

Information for administration of IMP is described in [Section 9.1](#)

#### **7.5 Prior and Concomitant Medications**

Data will be summarized for the overall population and by country, by treatment group, for all TEV-48125-treated subjects, and overall for the RS.

All prior and concomitant medications collected via case report form will be coded using the World Health Organization dictionary of medical codes (WHO Drug Dictionary Enhanced B2 March 2017). The number and percentage of subjects with prior medications and concomitant medications will be summarized by medication class and preferred name. Subjects are counted only once in each medication class category, and only once in each preferred name category. Prior medications will include all medications taken prior to the first dose of IMP. Concomitant medications will include all medications taken after the first dose of IMP.

The subset of prior medications and concomitant medications will be summarized for the following categories.

- Prohibited and restricted medications for preventive treatment of migraine medication

- Triptans and ergots for treatment of acute migraine
- Non-steroidal anti-inflammatory drugs (NSAIDs) for treatment of acute migraine
- Opioids for treatment of acute migraine

Additionally, the number and percentage of subjects with restricted concomitant medications (preventive treatment of migraine medications, Table 4.1.2-1 in the protocol) used at baseline will also be summarized.

## **7.6 Protocol Deviations**

The number and percentage of subjects with any major protocol deviations and each classification will be provided in each trial site and overall site by treatment group, for all TEV-48125-treated subjects, and overall for the RS.

## **8 Efficacy Analysis**

The FAS will be used for all efficacy analyses. Summaries will be presented by treatment group, unless otherwise noted. Descriptive statistics for all efficacy data will be presented by month (or week) and overall for the 12-week period. Descriptive statistics will include number of subjects, mean, SD, median, minimum, and maximum.

### **8.1 Primary Endpoint**

#### **8.1.1 Primary Analysis**

The primary efficacy endpoint is mean change from baseline in the monthly average number of headache days of at least moderate severity during the 12-week period after the first dose of IMP.

The primary endpoint will be analyzed using an analysis of covariance (ANCOVA) model. The model will include treatment, sex, country, and baseline preventive medication use as fixed effects and baseline number of headache days of at least moderate severity and years since onset of migraines as covariates. Two-sided 95% confidence intervals and p-values will be constructed for the least squares (LS) mean differences between each TEV-48125 group and the placebo group.

The following sample SAS code pertains to the primary analysis.

```
proc mixed;  
  class TREATMENT SEX PRVMBASE CONTRY;  
  model CHG = BASE TTMIG PRVMBASE SEX TREATMENT CONTRY /s;
```

```
lsmeans TREATMENT /pdiff cl alpha = 0.05;
ods output diffs = DIFFS lsmeans = LSMEANS;
run;
*PRVMBASE: Baseline preventive medication use
*TTMIG      : Years since onset of migraines
```

Multiplicity problems will be avoided using a closed testing procedure. If superiority of the TEV-48125 675/225/225 mg group to the placebo group is confirmed at a two-sided significance level of 0.05, then the TEV-48125 675 mg/placebo/placebo group vs the placebo group will be tested at a two-sided significance level of 0.05.

## 8.1.2 Sensitivity Analyses

### 8.1.2.1 Wilcoxon Rank-sum Test

The primary endpoint will be also analyzed using Wilcoxon rank-sum test to compare each TEV-48125 group vs the placebo group.

### 8.1.2.2 Analysis With Multiple Imputation Method

Regarding the primary endpoint, when the monthly average number of headache days of at least moderate severity during the 12-week period after the first dose of IMP is not missing, but any of the monthly number of headache days of at least moderate severity during the 4-week period after each dose of IMP (ie, Month 1, Month 2, and Month 3) is missing, the multiple imputation (MI) method will be applied to impute the missing data for Month 1, Month 2, or Month 3 and the primary endpoint will be calculated as the average of Month 1, Month 2, and Month 3. The data will be processed by the following steps.

- If a subject has partial electronic headache diary data for a month, ie, <10 days of data, a value for that month will be considered missing before the MI procedure.
- Subjects in each TEV-48125 group who are withdrawn early for reasons of adverse events (AEs) or lack of efficacy will be assigned to the placebo group and their missing values will be imputed using data from the placebo-treated subjects.
- The SAS MI procedure will be run to create 100 complete datasets.
- Within each imputed data set, for a subject who has partial, eg, X days ( $X < 10$ ), electronic headache diary data for a month, the monthly value will be replaced by 
$$\sum (\text{observed days of at least moderate severity}) + (28 - X) * \text{imputed value} / 28$$
- The monthly average number of headache days of at least moderate severity during the 12-week period after the first dose of IMP will be the average of the Month 1, Month 2, and Month 3 values.

Each dataset including the monthly average during the 12-week period will be analyzed using the same ANCOVA model as described in [Section 8.1.1](#). The LS means and standard errors (SE) from each analysis will be output to a SAS data set. The SAS MIANALYZE procedure will be used to generate the final LS means ( $\pm$  SE) for the treatment groups and the treatment differences (each TEV-48125 group – placebo group) as well as the p-values associated with treatment differences. The 95% confidence intervals for the treatment differences will also be constructed.

